2.7.4 Other safety data

2.7.4.1 ECG and cardiac imaging data

PR, QRS, QT, QTcF, RR intervals, and mean heart rate will be obtained from triplicate 12-lead ECGs for each participant during the study. ECG data will be read and interpreted centrally.

All ECG data will be listed by participant and visit/time, abnormalities will be flagged. Summary statistics will be provided by visit/time.

| Novartis | Confidential | Page 43 of 54 |
|----------|--------------|------------------------|
| SAP | | Study No. CLOU064A1301 |

In case multiple measurements on ECG are done for some visits, for numeric measurements, the mean of the scheduled measurements will be used. For ECG overall interpretation, most common interpretation (normal/abnormal) of the three assessments taken will be used. At visits with pre and post dose assessments, they will be presented separately.

A shift table from baseline to the worst post-baseline value will be presented based on the overall ECG interpretation.

The number and percentage of participants with newly occurring of the following criteria after baseline will be summarized:

- QT interval > 500 msec
- QTc (Fridericia's) interval > 450 msec (males), QTc (Fridericia's) interval > 460 msec (females)
- QTc (Fridericia's) interval change from baseline > 30 <60 msec, >= 60 msec
- PR interval > 250 msec
- PR interval > 250 msec and PR interval increase from baseline > 25%
- QRS duration >110 <=120 msec, >120 msec
- QRS duration > 120 msec and QRS duration increase from baseline > 25%

For notable summary tables, all post-baseline visits including unscheduled visits will be considered in the analysis.

2.7.4.2 Vital signs

All vital signs data will be listed by participant, and visit/time and if ranges are available, abnormalities (and relevant changes) will be flagged. Summary statistics will be provided by visit.

For by-visit summary tables, scheduled visits (including remapped visits following the assessment window in Section 2.1.1.4) will be considered in the analysis. Unscheduled visits will not be included.

For notable summary tables, all post-baseline visits including unscheduled visits will be considered in the analysis.

Analysis in vital sign measurement using descriptive summary statistics for the change from baseline for each post baseline visit will be performed. Change from baseline will only be summarized for participants with both baseline and post baseline values and will be calculated as:

```
change from baseline = post baseline value – baseline value
```

The number and percentage of participants with newly occurring clinically notable vital signs changes from baseline will be presented. Clinically notable vital sign results are provided in Table 2-11 below.

| Novartis | Confidential | Page 44 of 54 |
|----------|--------------|------------------------|
| SAP | | Study No. CLOU064A1301 |

| Table 2-11 Clinically notable changes in vital si | gns |
|---|-----|
|---|-----|

| Vital sign (unit) | Clinically notable criteria | |
|---------------------------------|-----------------------------|--|
| Systolic blood pressure (mmHg) | < 90 mmHg | |
| | ≥ 140 mmHg | |
| Diastolic blood pressure (mmHg) | < 60 mmHg | |
| | ≥ 90 mmHg | |
| Pulse (bpm) | < 50 bpm | |
| | > 100 bpm | |

For notable summary tables, all post-baseline visits including unscheduled visits will be considered in the analysis.

Dermatology Life Quality Index (DLQI)

For the following DLQI assessments, summary statistics will be presented on the FAS. The DLQI consists of 10-items, and the total score of the DLQI is calculated based on the developers' rules (possible range 0-30). For the total score derivation, if there was only one item left unanswered, the score of that item is imputed to 0 and then the total score is calculated accordingly. If there were two or more items left unanswered, then the total score is considered as missing. If the total score is missing, it will be handled without imputation and all available data will be used for the analysis.

• DLQI = 0-1: the proportion of participants achieving DLQI = 0-1 response by visit

Angioedema Activity Score (AAS)

For the following AAS assessments based on AAS eDiary, summary statistics will be presented on the FAS. See Section 2.6.1 for derivation of AAS7 score and AAS7 =0 response.

| Novartis SAP | Confidential | Page 46 of 54 Study No. CLOU064A1301 |
|-----------------|--------------|---|
| | | |
| | | |
| | | |
| | | |
| | | |
| | | |
| | | |
| | | |
| | | |
| | | |
| | | |
| | | |
| | | |
| | | |
| | | |
| | | |
| | | |
| | | |
| | | |
| | | |
| | | |
| | | |
| | | |
| | | |
| | | |
| | | |
| | | |
| | | |
| | | |

| Novartis | Confidential | Page 47 of 54 |
|--|--------------|------------------------|
| | | Study No. CE00004A1301 |
| | | |
| | | |
| | | |
| | | |
| | | |
| | | |
| | | |
| | | |
| | | |
| | | |
| | | |
| | | |
| | | |
| | | |
| | | |
| | | |
| | | |
| | | |
| | | |
| | | |
| | | |
| | | |
| | | |
| i la | | |
| | | |
| | | |
| | | |
| | | |
| | | |
| | | |

2.13 Interim analysis

See Section 1.1.

3 Sample size calculation

Since CSU is a chronic disease, and remibrutinib is expected to be administered over a long period, safety in long-term treatment needs to be confirmed. "Regarding sample size and treatment period required to assess safety at the clinical study stage of a new drug anticipated to be administered for a non-fatal disease over a long period" (Notification No. 592 of the Pharmaceuticals and Cosmetics Division, Pharmaceutical Affairs Bureau, MHLW, dated 24-May-1995), this notification requires to collect safety data of at least 100 Japanese patients who receive the drug over one year. CLOU064A2201E1 study was planned to collect efficacy and safety data of about 33 Japanese CSU participants exposed to remibrutinib greater than or equal to the application dose for one year and CLOU064A2301 study was planned to collect efficacy and safety data of about 15 Japanese CSU participants exposed to remibrutinib of the application dose for one year. Therefore, this study CLOU064A1301, is designed to obtain safety data of approximately 70 Japanese CSU participants exposed to remibrutinib at the application dose for one year. Since approximately 30% screening failure rate and approximately 15% dropout rate are expected, approximately 100 patients will need to be screened in order to collect approximately 70 participants who enter the treatment period and to collect a total of approximately 60 completed participants.

4 Change to protocol specified analyses

No change from protocol specified analysis.

5.1 Imputation rules

5.1.1 Study drug

Partial dose date is not allowed in data collection.

5.1.2 AE date imputation

Imputation for AE end date:

1. If the AE end date 'month' is missing, the imputed end date should be set to the earliest of the (last visit date, 31DECYYYY, date of death).

2. If the AE end date 'day' is missing, the imputed end date should be set to the earliest of the (last visit date, last day of the month, date of death).

3. If the AE end date 'year' is missing or the AE is ongoing, the end date will not be imputed.

Imputation for AE start date:

Before imputing AE start date, find the AE start reference date as below:

- If the (imputed) AE end date is complete and the (imputed) AE end date < the treatment start date then AE start reference date = min (informed consent date, earliest visit date)
- Else AE start reference date = the treatment start date

1. If the AE start date 'year' is missing, the date uncertainty is too high to impute a rational date. Therefore, if the AE start date 'year' is missing, the imputed AE start date is set to NULL.

2. If the AE start date 'year' is less than the treatment start date 'year', the AE started before treatment. Therefore:

- If the AE start date 'month' is missing, the imputed AE start date is set to the mid-year point (01JulYYYY)
- Else if the AE start date 'month' is not missing, the imputed AE start date is set to the mid-month point (15MONYYY)

3. If the AE start date 'year' is greater than the treatment start date 'year', the AE started after treatment. Therefore:

• If the AE start date 'month' is missing, the imputed AE start date is set to the year start point (01JanYYYY)

| Novartis | Confidential | Page 50 of 54 |
|----------|--------------|------------------------|
| SAP | | Study No. CLOU064A1301 |

• Else if the AE start date 'month' is not missing, the imputed AE start date is set to the later of the (month start point (01MONYYYY), AE start reference date + 1 day)

4. If the AE start date 'year' is equal to the treatment start date 'year':

- And the AE start date 'month' is missing, the imputed AE start date is set to the AE reference start date + 1 day
- Else if the AE start date 'month' is less than the treatment start date 'month', the imputed AE start date is set to the mid-month point (15MONYYY)
- Else if the AE start date 'month' is equal to the treatment start date 'month' or greater than the treatment start date 'month', the imputed AE start date is set to the later of the (month start point (01MONYYYY), AE start reference date + 1 day)

If complete (imputed) AE end date is available and the imputed AE start date is greater than the (imputed) AE end date, then the imputed AE start date should be set to the (imputed) AE end date.

5.1.3 Concomitant medication date imputation

Imputation for concomitant medication (CM) end date:

1. If the CM end date 'day' is missing and the CM end date 'month' and 'year' are not missing, the imputed CM end date is set to the earlier of the (treatment end date and last day of the month).

2. If the CM end date 'day' and 'month' are missing and the CM end date 'year' is not missing, the imputed CM end date is set to the earlier of the (treatment end date and end of the year (31DECYYYY)).

3. If the imputed CM end date is less than the CM start date, use the CM start date as the imputed CM end date.

Imputation for CM start date:

1. If the CM start date 'year' is missing, the imputed CM start date is set to one day prior to the treatment start date.

2. If the CM start date 'year' is less than the treatment start date 'year', the CM started before treatment. Therefore:

- If the CM start date 'month' is missing, the imputed CM start date is set to the mid-year point (01JulYYYY)
- Else if the CM start date 'month' is not missing, the imputed CM start date is set to the mid-month point (15MONYYYY)

| Novartis | Confidential | Page 51 of 54 |
|----------|--------------|------------------------|
| SAP | | Study No. CLOU064A1301 |

3. If the CM start date 'year' is greater than the treatment start date 'year', the CM started after treatment. Therefore:

- If the CM start date 'month' is missing, the imputed CM start date is set to the year start point (01JanYYYY)
- Else if the CM start date 'month' is not missing, the imputed CM start date is set to the month start point (01MONYYYY)

4. If the CM start date 'year' is equal to the treatment start date 'year':

- And the CM start date 'month' is missing or the CM start date 'month' is equal to the treatment start date 'month', the imputed CM start date is set to one day prior to the treatment start date.
- Else if the CM start date 'month' is less than the treatment start date 'month', the imputed CM start date is set to the mid-month point (15MONYYY)
- Else if the CM start date 'month' is greater than the treatment start date 'month', the imputed CM start date is set to the month start point (01MONYYY)

If complete (imputed) CM end date is available and the imputed CM start date is greater than the (imputed) CM end date, then the imputed CM start date should be set to the (imputed) CM end date.

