2.4 Treatments (study treatment, rescue medication, concomitant therapies, compliance)

2.4.1 Study treatment / compliance

The analysis of study treatment data and the analysis of duration of study will be based on the Safety Set.

Duration of exposure (days) will be defined as last dose of study treatment – first dose of study treatment + 1.

Duration of study (days) will be defined as last study visit – first dose of study treatment + 1.

The duration of exposure and the duration of study in weeks will be derived as follows:

- Duration of exposure (weeks) = duration of exposure (days) / 7
- Duration of study (weeks) = duration of study (days) / 7
- Duration of exposure (years) = duration of exposure (days) / 365.25
- Duration of study (years) = duration of study (days) / 365.25

The duration of exposure to study treatment will be computed without excluding temporary treatment interruptions.

The duration of exposure and duration of study in weeks to LOU064 25mg will be summarized.

The number of participants with the duration of exposure and the duration of study of at least certain thresholds (e.g., any exposure, >0 - <2 weeks, ≥ 2 weeks - <4 weeks, ≥ 4 weeks - <8 weeks, ≥ 8 weeks - <12 weeks, ≥ 12 weeks - <16 weeks, ≥ 16 weeks - <20 weeks, ≥ 20 weeks - <20 w

| Novartis | Confidential | Page 31 of 54 |
|----------|--------------|------------------------|
| SAP | | Study No. CLOU064A1301 |

<24 weeks, ≥24 weeks - <32 weeks, ≥32 weeks - <40 weeks, ≥40 weeks - <52 weeks and ≥52 weeks) will be displayed.

2.4.2 **Prior**, concomitant and post therapies

Medications will be identified using the WHODrug including Anatomical Therapeutic Chemical (ATC) code. In the summary tables, medications (including background or rescue medications) will be presented in alphabetical order, by ATC codes and preferred term. Tables will show the overall number and percentage of participants receiving at least one drug of a particular ATC code and at least one drug in a particular preferred term.

Prior medications are defined as drugs taken and stopped prior to first dose of study medication. Any medication given at least once between the day of first dose of study treatment and the last day of study visit will be a concomitant medication, including those which were started prebaseline and continued into the treatment period. Prior or concomitant medication will be identified based on recorded or imputed start and end dates of medication taking.

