2.6.3 Handling of intercurrent events

Participants who discontinue from study treatment early due to any reason will be encouraged to stay in the study following the procedures. Every effort will be made to continue to follow participants who discontinued from study treatment up to Week 12. These are considered as RDO participants. If no RDO data was collected after study treatment permanent discontinuation, missing data will be handled without imputation and all available data will be used for the analysis.

| Novartis | Confidential | Page 38 of 54 |
|----------|--------------|------------------------|
| SAP | | Study No. CLOU064A1301 |

The analysis will account for different intercurrent events as explained in the following:

- Discontinuation of study treatment prior to Week 12 due to any reason: ignore, i.e., data collection will be maintained and available measurements post-treatment discontinuation will be used as if they had been obtained under the treatment: RDO data collected after study treatment discontinuation will be used for analysis (Treatment policy strategy).
- Treatment non-compliance (interruption), switch of background medication, or intake of rescue medication as per protocol prior to Week 12: ignore, i.e., data collected after these events will be used for analysis (Treatment policy strategy).
- Intake of strongly confounding prohibited medication (e.g., biologics treatment at any time before Week 12 (as identified by PD M-COMD03), cyclosporine after Week 8 to Week 12 (as identified by PD M-COMD04), systemic corticosteroids after Week 8 to Week 12 (as identified by PD M-COMD04)): measurements after this event will be excluded from the analysis and will be imputed using the worst value of the endpoint (e.g., 42 for UAS7 score at Week 12, 21 for ISS7 or HSS7 score) (Composite strategy (irrespective of potential occurrence of other intercurrent events)). Note: for the endpoint of UAS7 ≤6 at Week 2, intake of cyclosporine or systemic corticosteroids will not be considered.
- Intake of other prohibited medication prior to Week 12: ignore, i.e., Data collected after these events will be used for analysis (Treatment policy strategy).

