In addition to liver enzyme test abnormalities, for participants meeting the criteria [ALT or AST >5x ULN] or [ALT or AST>3xULN & TBL >2xULN & ALP <2xULN], graphical case (per participant) representation to include graph of liver enzymes over time (ALT, AST, TBL, ALP, based on xULN) with treatment exposure and concomitant medications, will be provided if any case.

Table 2-9Liver enzyme abnormalities

| | · · · · · · · · · · · · · · · · · · · |
|--------------------------|--|
| Parameter | Criterion |
| ALT | >3xULN; >5xULN; >8xULN; >10xULN; >20xULN |
| ALT or AST | >3xULN; >5xULN; >8xULN; >10xULN; >20xULN |
| (ALT or AST) & TBL | >3xULN & (TBL>1.5xULN; >2xULN) |
| (ALT or AST) & INR | >3xULN & INR>1.5 |
| TBL | >1xULN; >1.5xULN; >2xULN |
| ALP | >1.5xULN; >2xULN; >5xULN |
| ALP & TBL | >3xULN; >5xULN & TBL>2xULN |
| (ALT or AST) & TBL & ALP | ALT or AST>3xULN & TBL>2xULN & ALP<2xULN (Potential Hy's Law) |

Table 2-10 Specific renal alert criteria

| Parameter | Notable criteria |
|-----------------------------------|---|
| Serum creatinine | Increase 25% - <50% (%change from baseline) |
| | Increase $\geq 50\%$ |
| Dipstick proteinuria | \geq 3 + (Newly occurring) |
| Dipstick hematuria (occult blood) | ≥ 3 + (Newly occurring) |

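### SAP 5.1.3 caps a partial concomitant-medication end date at the end of treatment, not the last visit, so an off-drug end date can fall before the month recorded on the CRF

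*SAP*

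**What the plan says.** SAP 5.1.3 has three end-date items, four start-date items and a closing paragraph.

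- End-date item 1 (day missing): "the imputed CM end date is set to the earlier of the (treatment end date and last day of the month".
- End-date item 2 (day and month missing): "the imputed CM end date is set to the earlier of the (treatment end date and end of the year (31DECYYYY".
- End-date item 3: "If the imputed CM end date is less than the CM start date, use the CM start date as the imputed CM end date".
- Closing paragraph, where an imputed start is later than the end date: "then the imputed CM start date should be set to the (imputed) CM end date".

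SAP 5.1.4 applies the same rules to non-drug therapies.

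Four other places bear on this:

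- For an adverse event with the end day missing, SAP 5.1.2 says "the imputed end date should be set to the earliest of the (last visit date, last day of the month, date of death".
- SAP 2.4.2 says that any drug given at least once "between the day of first dose of study treatment and the last day of study visit will be a concomitant medication". It classifies medication by recorded or imputed dates.
- Protocol 9.1.1 asks participants who stop drug before Week 12 to keep attending up to Week 12, sends later stoppers to the safety follow-up visit, and collects new and concomitant treatments after the stop. SAP 1.1 gives completers who do not enter the extension four drug-free weeks.
- The SAP does not define *treatment end date*. The footnote to protocol Table 6-2 takes end of treatment as the day of the last dose, and SAP 2.4.1 ends exposure at the last dose.

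**The concern.** Medication is collected for some weeks after the last dose, but a partial end date may not be imputed later than that dose. A CRF entry that says a drug stopped in a later month is then turned into a date which the CRF itself rules out. Adverse events and co-medications are also dated by different limits.

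The stake is the reading of individual cases. Safety is the primary objective in about 70 participants. For marked liver-enzyme elevations, SAP 2.7.3 plans a per-participant "graph of liver enzymes over time (ALT, AST, TBL, ALP, based on xULN) with treatment exposure and concomitant medications". A co-medication that in fact continued would be drawn as stopping on the day remibrutinib stopped, so the graph would show two withdrawals where there was one.

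The sensitivity analysis of adverse events of special interest (SAP 2.5.5) keeps only data before intake of certain drugs. BCRP substrates are found there by medication name on the CRF, so their intake date has to come from the medication record.

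**Working it through.** The plan states no figure to reproduce, so the check applies the rules to dates.

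**Step 1. One early stopper.** Assume first dose 1 Jun 2022, last dose 5 Jul 2022 (Day 30 + 5 = 35) and last visit 24 Aug 2022 (Day 30 + 31 + 24 = 85, the Week 12 visit). The medication end is recorded as August 2022, day unknown.

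Current rule: end = min(last dose, month end) = min(5 Jul, 31 Aug) = 5 Jul. With a last-visit cap: min(24 Aug, 31 Aug) = 24 Aug.

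| Start of medication | Current result | With last-visit cap |
|---|---|---|
| Before last dose | end 5 Jul: wrong month | end 24 Aug |
| Complete, 20 Jul | item 3 resets end to 20 Jul: wrong month, one-day course | end 24 Aug |
| Complete, 3 Aug | item 3 resets end to 3 Aug: right month, one-day course | end 24 Aug |
| Also August, day unknown | start and end both 5 Jul | start 1 Aug, end 24 Aug |

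In the last row, printed order gives end = 5 Jul. No complete start exists yet for item 3 to compare. Start-date item 4 then gives 1 Aug, and because 1 Aug is after 5 Jul the closing paragraph moves the start to 5 Jul. If the start were imputed first and item 3 then applied, both dates would be 1 Aug even under the present cap.

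**Step 2. Other cases.**

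- Completer, start before last dose, last dose 31 May 2023, end June 2023: imputed 31 May, wrong month. With last visit 29 Jun, the last-visit cap gives 29 Jun.
- Last dose 2 Jun 2023, end June 2023: imputed 2 Jun. This is early but inside the recorded month, so nothing is contradicted.
- Year-only end 2023, last dose 20 Dec 2022: imputed 20 Dec 2022, wrong year.

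**Step 3. Behaviour of the rule, not of the trial.** Assume the last dose is equally likely on any day of a year and the true end is 1 to 28 days later, each equally likely.

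- Start before the last dose: an end k days later lies in a later month with probability k × 12/365. The mean of k is 14.5, so the wrong-month share is 14.5 × 12/365 = 0.48.
- Complete start equally likely on any day from 1 to k after the last dose: the share for a given k is (k − 1)/2 × 12/365. The mean of (k − 1)/2 is 6.75, so the share is 6.75 × 12/365 = 0.22.

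An enumeration over all last-dose days gave the same two values, and 0 with a last-visit cap. These are shares of off-drug partial end dates under the stated assumption. The documents do not say how many such dates there are.

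**Step 4. Liver graph.** In the first row of the table, the drug is known to have continued at least to 1 Aug, which is 27 days after the last dose. The graph would end it on 5 Jul.

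**Step 5. BCRP substrate.** Assume first dose in 2022, last dose 8 Feb 2023, last visit 8 Mar 2023, substrate recorded March 2023 to March 2023, and an event of special interest on 20 Feb. The event is on treatment, since 8 Feb + 28 days = 8 Mar. The start is imputed as 1 Mar, the end as min(8 Feb, 31 Mar) = 8 Feb, and the closing paragraph moves the start to 8 Feb. The event now falls after intake and would be excluded, although the recorded month puts intake after the event. With the proposed change the start stays at 1 Mar, the end is min(8 Mar, 31 Mar) = 8 Mar, and the event is kept.

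**The case against.** The case for leaving the rule alone is mainly that little depends on it, and most of that stands.

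- **Week 12 composite.** A reader might infer that a steroid course running past Week 8 would be dated before Week 8 and missed. SAP 2.6.3 does not work that way: it refers to "systemic corticosteroids after Week 8 to Week 12 (as identified by PD M-COMD04", and identifies biologics and cyclosporine by deviation codes too. Nothing says that imputed medication dates decide the call. It would likewise be tempting to compute 42/70 = 0.6 UAS7 points or 1/70 = 1.4 percentage points for each wrong call; those figures need the same unproven link.
- **Treatment-emergent events.** A reader might infer harm to the 28-day post-dose window. That window classifies adverse events and safety assessments. Adverse-event dates come from 5.1.2, and medication end dates do not enter.
- **Prior or concomitant status.** The capped end, and a start moved to the last dose, remain on or after first dose, so the drug stays concomitant. The medication tables count participants, not durations.
- **Special-interest analysis.** It is conditional on an incidence above that of the A2201E1 study plus 20%, and the text then says only that it may be done. Apart from BCRP substrates, the listed drugs are identified by deviation codes. Nor does the plan say whether a substrate first taken after the last dose should count at all.
- **Rarity.** Participants who roll over have no off-drug period here, missing values are queried (protocol 11.2), and liver graphs are drawn only if a case occurs.
- **Conflicting resets.** A reader might infer that item 3 and the closing paragraph leave the result undetermined. Read literally, the closing paragraph deals with an imputed start and comes last, so the text does give a result. For two partial off-drug dates, it is the wrong one.

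None of this makes the imputed date right. No passage corrects the cap, and the neighbouring rule in 5.1.2 shows the consistent choice.

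**Conclusion.** Wrong as written, minor. Where the recorded end month or year is later than that of the last dose, SAP 5.1.3 imputes an end date before the recorded period, unless item 3 resets it to a complete start date in that period. Where both dates are partial and after the last dose, the start is moved back to the last dose as well.

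Two outputs can be affected: co-medication bars in the per-participant liver graphs, and the timing of BCRP substrates in the conditional special-interest analysis. The problem is confined to participants with off-drug follow-up and partial dates, and all the analyses are descriptive. No numeric magnitude is supported, because the documents do not give the number of partial dates.

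The conclusion assumes that *treatment end date* means the last dose. If the team means something else, the SAP should define it, and the size of the error changes accordingly.

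**What to change.** In SAP 5.1.3 end-date items 1 and 2, and so in 5.1.4, replace the treatment end date with the last visit date, or the date of death or data cut-off if earlier. This follows the logic of 5.1.2.

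Add that when both dates are partial the start is imputed first and item 3 then applies, so that an imputed end does not precede the recorded month.

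Leave start-date item 4 unchanged. It deliberately places some starts on the day before first dose, which can lie in the previous month, so a general ban on leaving the recorded month would override it.

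The cost is a short SAP edit and a change to the date-derivation program. No new data are needed.
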